followed for 30 days for adverse event monitoring (serious adverse events will be collected for 90 days after the end of treatment as described in Section 7.2.3.1). Subjects who discontinue for reasons other than progressive disease will have scheduled post-treatment follow-up monitoring for disease status until disease progression, initiating a non-study cancer treatment, withdrawing consent or becoming lost to follow-up. After documented disease progression each subject will be followed by chart review, clinic visits, or telephone contact for overall survival until death, withdrawal of consent, or the end of the study, whichever occurs first.

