7.1.1.5.4 Subsequent Anti-Cancer Therapy Status

The investigator or qualified designee will review all new anti-neoplastic therapy initiated after the last dose of trial treatment. If a subject initiates a new anti-cancer therapy within 30 days after the last dose of trial treatment, the 30 day Safety Follow-Up visit must occur before the first dose of the new therapy. Once new anti-cancer therapy has been initiated or if transition to palliative/end of life care such as Hospice enrollment occurs, the subject will move into Survival Follow-Up Phase.

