8.3 Definition of Study Endpoints

8.3.1 Primary Endpoint

The primary endpoint was amended to be overall response rate (**ORR**) with addition of Expansion Cohort, based upon the promising responses observed during Stages 1 and 2 (Safety and Efficacy Cohorts). **ORR** is defined as the proportion of subjects with RECIST 1.1-measurable disease at study entry who have a complete response (CR) or partial response (PR) (confirmed + unconfirmed) using RECIST 1.1¹ at any time during the main study. Measurable disease has been added as a required inclusion criterion for Expansion Cohort eligibility. Re-induction and Second Course ORR (rORR, sORR) will be determined based upon response after first dose of re-induction or first dose of Second Course. Subjects with measurable disease at study entry who have unknown or missing response information will be treated as non-responders. Subjects with non-measurable disease at study entry will be excluded from ORR and DOR analyses.

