8.3.2 Secondary Endpoints

- 1) **Safety** endpoint assessment is described in Section 7.2. The safety endpoints are AEs graded using CTCAE (Version 4.0) criteria. Safety will be assessed by quantifying the toxicities and grades experienced by subjects who have received pembrolizumab plus GM-CSF induction, including SAEs and ECIs. Other safety endpoints include laboratory safety assessments, ECOG performance status, Child Pugh score, vital signs, and physical examinations. The incidence and frequency of dose reduction, treatment delays, and discontinuation for lack of tolerability will be quantified. Re-induction and Second Course safety events will be addressed in the same manner.

- 2) **Tumor PD-L1 status** will be measured by IHC and classified as positive or negative by central laboratory testing (QualTek Laboratories) using pre-specified cut-points.
- 3) A key secondary endpoint is %PFS6 (formerly primary endpoint, changed by amendment with addition of Expansion Cohort). For each patient, PFS will be calculated in days and months from date of first dose of protocol therapy to date of first documented radiographic and/or clinical disease progression or death from any cause. For patients removed from study for other reasons than progression or death, PFS will be censored at the date last known to be progression-free. See Section 5.9 for Replacement policy for non-evaluable patients. The %PFS6 will be calculated as the proportion of evaluable patients progression-free at 6 months. Censored patients without progression will be treated as non-progression statistically and counted in denominator toward %PFS6.

For patients who continue on treatment despite radiographic progression based upon impression of clinical benefit an/or assessment with possible pseudo-progression or a delayed response⁴⁶ (see Section 5.8), PFS will be calculated at time of first documented progression after subsequent imaging confirms progression. If subsequent imaging does not demonstrate progression, then a PFS event will not have occurred and the patient will continue with scheduled imaging assessments per protocol to determine PFS.

Re-induction and Second Course PFS (rPFS, sPFS) will be calculated in months from date of first dose of re-induction or Second Course to date of first documented radiographic and/or clinical disease progression during or after re-induction or Second Course, or death from any cause. RPFS and sPFS will be reported descriptively.

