8.4 Sample Size and Accrual Rate

8.4.1 Sample Size

For the primary endpoint of ORR, a sample size of 37 response-evaluable subjects will provide power of 77% with 2-sided 5% alpha and 88% with 1-sided 5% alpha to show ORR improvement from H_0 of 5% to H_1 of 20%, under protocol treatment. Based upon a subset with non-measurable disease enrolled to Stages 1 and 2 before amendment requiring RECIST 1.1-measurable tumors for enrollment to Expansion Cohort, along with potential for dropout in this population with comorbidity of biliary obstruction and liver disease, it is estimated that total enrollment of 42 subjects will include at least 37 response-evaluable subjects.

The key secondary endpoint of %PFS6 was previously the primary endpoint for Stages 1 and 2, prior to amendment adding Expansion Cohort, which also changed to primary endpoint of ORR based upon the promising response rate observed in Stages 1 and 2. For the key secondary endpoint of PFS, an expected overall study PFS-evaluable sample size of at least 40 patients will have power 78% with 2-sided alpha 5% and power 87% with 1-sided alpha to show PFS improvement from H_0 of 20% to H_1 of 40% on protocol therapy.

Pre-amendment, a Simon's 2 stage design was employed to determine if adequate efficacy was observed in Stage 1 to warrant proceeding to Stage 2. The pembrolizumab/GM-CSF combination was considered worthy of additional investigation if the true %PFS6 is 50%, and hence the alternative hypothesis, $\%PFS_1=0.50$. Therefore assuming an α error probability of 5%, and a β error of 20%, the first stage had 9 patients. If ≤ 2 of 9 had been observed progression-free, the study would not proceed to second stage. Since ≥ 3 of 9 patients are observed progression-free at 6 months (4/9 achieved PFS6 in Stage 1), enrollment continued to the second stage with 18 additional patients, with a goal of at least 24 evaluable patients (with planned over-enrollment of 3 additional patients to account for expected 10% dropout rate). If ≤ 9 patients are observed progression-free at 6 months out of 24 evaluable patients by the end of second stage, then no further investigation of the drug is warranted under this PFS6 hypothesis. Conversely, if ≥ 10 patients are progression-free at 6 months among Stages 1 and 2 subjects, the study would be considered positive for the hypothesis: H_0 : $\%PFS_0 < 25\%$ versus H_a : $\%PFS_1 > 50\%$.

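### %PFS6 counts evaluable patients censored before 6 months as 6-month successes, so the key secondary endpoint is biased upward or, at best, unchanged

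*Combined protocol and SAP*

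**What the plan says.** Section 8.3.2, item 3, counts PFS from first dose to the "date of first documented radiographic and/or clinical disease progression or death from any cause". It then says: "For patients removed from study for other reasons than progression or death, PFS will be censored at the date last known to be progression-free". %PFS6 is the share of evaluable patients who are progression-free at 6 months, with this rule for censoring: "Censored patients without progression will be treated as non-progression statistically and counted in denominator toward %PFS6".

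Two other parts of the plan take a different line. For ORR, Section 8.3.1 says: "Subjects with measurable disease at study entry who have unknown or missing response information will be treated as non-responders". The Stage 1-2 decision rule in Section 8.4.1 is written for how many "patients are observed progression-free at 6 months out of 24 evaluable patients by the end of second stage".

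The set of patients evaluable for PFS6 is not defined. Section 8.3.2 refers to Section 5.9 for non-evaluable patients. Section 5.9 gives an over-enrollment allowance and points to Section 8.6 for the analysis populations, but these stand in Section 8.5, and Section 8.5.2 defines evaluability for ORR only. Section 8.6.2.3 gives power for %PFS6 against 20%, while Section 8.6.2 makes secondary endpoints descriptive. Kaplan-Meier appears in Section 8.6.2.4 for medians and quartiles only.

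**The concern.** In a proportion of patients who are progression-free, treating a censored patient as not having progressed means counting a success. With no minimum follow-up, an evaluable patient last seen progression-free at week 10 scores the same as one scanned clear at 6 months.

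Such patients can arise. Under Section 5.8, disease monitoring after stopping treatment for another reason runs "until disease progression, initiating a non-study cancer treatment, withdrawing consent or becoming lost to follow-up". Under Section 7.1.1.5.4, "if transition to palliative/end of life care such as Hospice enrollment occurs, the subject will move into Survival Follow-Up Phase". These exits may be linked to worsening disease.

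%PFS6 was the primary endpoint and is now a key secondary one. There is no control arm to share the bias. If %PFS6 is tested, each early-censored patient adds to the false-positive risk. If it is descriptive, the estimate and its confidence interval move upward.

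**Working it through.** **Inputs.** H0 20%, H1 40%, 40 evaluable patients, stated power 87% (1-sided 5%) and 78% (2-sided 5%): Sections 8.4.1 and 8.6.2.3. The number of evaluable patients censored early, c, is not in the available text. The only dropout rate stated is 10% (Section 8.4.1), as an over-enrollment allowance for Stages 1 and 2.

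**1. The plan's own figures.** The plan names Fisher's exact test. The figures match a one-sample exact binomial with n = 40:

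- Cut-off 13 (1-sided 5%): P(X ≥ 13 | 0.2) = 0.0432; P(X ≥ 13 | 0.4) = 0.8715, stated as 87%.
- Cut-off 14 (upper tail 2.5%): P(X ≥ 14 | 0.2) = 0.0194; P(X ≥ 14 | 0.4) = 0.7888, stated as 78%.

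The cut-offs are reconstructed; the plan does not print them.

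**2. Direction.** Let s patients be observed progression-free at 6 months, c be censored earlier and d have an event by then, with n = s + c + d. The rule reports (s + c)/n = 1 − d/n. This is never below the true 6-month proportion in these patients, s/n, s/(n − c) or the Kaplan-Meier estimate. The excess over the true proportion lies between 0 and c/n. It is 0 only if c = 0 or every censored patient was in fact progression-free at 6 months.

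**3. Fixed number of automatic successes, the rest at 20%.** Mean displayed rate = (c + 0.2(40 − c))/40; error = P(Bin(40 − c, 0.2) ≥ 13 − c), and likewise for 14.

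| c | Mean %PFS6 | Error, cut-off 13 | Error, cut-off 14 |
|---|---|---|---|
| 0 | 20% | 4.3% | 1.9% |
| 1 | 22% | 7.4% | 3.6% |
| 2 | 24% | 12.2% | 6.2% |
| 4 | 28% | 28.4% | 16.8% |

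**4. Milder assumed model.** PFS is exponential with S(6) = 0.2. A fraction p of patients drops out at a time U uniform on 0-6 months, independent of PFS. Mean S(U) = 0.8/(−ln 0.2) = 0.4971. The displayed success probability is q = 0.2 + p(0.4971 − 0.2), the mean number censored early is 40 × p × 0.4971, and the error is P(Bin(40, q) ≥ cut-off).

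| Dropout p | Mean censored early | Mean %PFS6 | Error, cut-off 13 | Error, cut-off 14 |
|---|---|---|---|---|
| 5% | 1.0 | 21.5% | 7.1% | 3.5% |
| 10% | 2.0 | 23.0% | 10.9% | 5.7% |
| 20% | 4.0 | 25.9% | 21.8% | 13.1% |

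At 10% dropout, four or more early-censored patients occur in about 14% of trials and none in about 13%.

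**5. The opposite rule (censored early = not progression-free).** At a true 40%, power at cut-off 13 with fixed c is P(Bin(40 − c, 0.4) ≥ 13) = 84%, 81% and 74% for c = 1, 2 and 4. Under random dropout it is P(Bin(40, 0.4(1 − p)) ≥ 13) = 81%, 73% and 53% for 5%, 10% and 20%. At a true 20% the mean is 0.2(1 − p) = 19%, 18% and 16%.

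**6. Kaplan-Meier.** With random dropout it averages 20.0%. Suppose instead that 10% of patients who progress within 6 months are censored just before progression. A true 20% then shows as 0.2 + 0.1 × 0.8 = 28.0% under the present rule, 0.2^0.9 = 23.5% by Kaplan-Meier and 20.0% under the opposite rule.

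**The case against.** - **Wording.** The sentence names the denominator and not the numerator. It could be read as keeping censored patients in the denominator while crediting only those known to be progression-free. That reading leaves the words about treating them as non-progression without effect, so it is the weaker one. If it is what was meant, the text still needs correcting.
- **Dropout figure.** The 10% belongs to Stages 1 and 2, "with planned over-enrollment of 3 additional patients to account for expected 10% dropout rate", and Section 5.9 ties over-enrollment to non-evaluability. Part or all of it may lie outside the 40 evaluable patients. This stands: the 20% dropout row and the four-patient row have no source in the documents. Only the direction is established.
- **Few routes.** Clinical progression and death are PFS events, scans continue after treatment stops, and deaths are captured in survival follow-up. A move to hospice may already have been recorded as clinical progression. This stands, and it makes small counts the more plausible ones.
- **Test or description.** If %PFS6 is only descriptive, the shift is 1.5 to 3 points at 5-10% assumed dropout, against a standard error of √(0.2 × 0.8/40) = 6.3 points. This also stands, but the shift goes one way only and can be avoided.
- **Remedy.** Counting early censoring as failure biases downward under random dropout, where Kaplan-Meier does not. True, and a reason to report both. Kaplan-Meier in turn is too high when censoring precedes progression (step 6).
- **Evaluable set.** A definition requiring known 6-month status would make the rule inert. The available text has no such definition.

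**Conclusion.** The concern holds. As written, the rule credits a 6-month success to any evaluable patient censored earlier without progression, and nothing in Sections 5.9, 8.5.2, 8.6.2.3 or 8.6.2.4 prevents it. The direction, upward or zero, follows from the definition alone. The size depends on a count that the available text does not give, and with no early-censored patients there is no inflation. If %PFS6 is tested at the reconstructed 1-sided cut-off, one automatic success is enough to take the error above 5%. The primary ORR analysis is not touched. This should be fixed, but it does not put the trial's main conclusion at risk.

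**What to change.** Replace the sentence in Section 8.3.2. An evaluable patient is a %PFS6 success only with documented progression-free status at 6 months; all others, including those censored earlier, count as not progression-free. This matches the ORR rule.

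Also:

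- Define 'documented'. The nearest scheduled scan is week 24 (day 168 ± 7, so days 161-175), before 6 months at about day 183. One workable rule is a scan without progression at week 24 or later, plus confirmation at 6 months of no clinical progression or death.
- Define the PFS6-evaluable set independently of outcome, for example all treated patients, and correct the pointer in Section 5.9.
- Report the Kaplan-Meier 6-month PFS with 95% CI as a supporting estimate, noting that it assumes non-informative censoring. Add a sensitivity analysis excluding patients of unknown status.
- State whether %PFS6 is tested (Section 8.6.2.3) or descriptive (Section 8.6.2).
- Record the date and reason of the change, and report the result under the present rule as well.

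The cost is SAP text and a few tabulations, with some loss of power (step 5) and possibly a lower reported rate. The change is data-aware: Stage 1 PFS6 is known (4 of 9), and Stage 2 enrollment ended in September 2017, more than 6 months before this version's date of 10/01/2019. Reporting both rules side by side shows how much the choice matters.

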4.3.6.2 Secondary Efficacy Endpoints

Proportion with PFS at 6 months (%PFS6) %PFS6 will be a key secondary endpoint for the overall study. In advanced biliary cancers treated with standard \geq 2nd line systemic chemotherapies, retrospective studies report median PFS of only approximately 2 to 3 months (corresponding to %PFS6 of approximately 20% (H_0) assuming normal distribution).^{2,4,10} A target %PFS6 of 40% (H_1) on treatment with pembrolizumab plus induction GM-CSF would represent a clinically meaningful improvement. Locally-assessed RECIST 1.1¹ will be used to determine progression.

Overall survival will be measured as another key secondary endpoint with the hypothesis that the median overall survival will be increased compared to a historical control median OS of 6.7 months from start of standard second line chemotherapy for advanced biliary cancers.⁶

An additional secondary efficacy endpoint is DOR, defined as time from first RECIST 1.1 response to disease progression in subjects who achieve a PR or better, as a clinically-relevant measure of efficacy. The duration of response or disease stabilization with 2nd line conventional chemotherapy in biliary tract cancers is very short, with median PFS only approximately 2-3

months on standard 2nd line therapies, and the majority of objective responses transient, lasting less than 6 months.^{2,37}

Re-induction and Second Course efficacy endpoints will also be described.

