5.8 Subject Withdrawal/Discontinuation Criteria

Subjects may withdraw consent at any time for any reason or be dropped from the trial at the discretion of the investigator should any untoward effect occur. In addition, a subject may be withdrawn by the investigator or the Study Chair if enrollment into the trial is inappropriate, the trial plan is violated, or for administrative and/or other safety reasons. Specific details regarding discontinuation or withdrawal are provided in Section 7.1.5 – Other Procedures.

A subject must be discontinued from the trial for any of the following reasons:

- The subject or legal representative (such as a parent or legal guardian) withdraws consent.
- Radiographic disease progression by RECIST 1.1.

Note: A subject may be granted an exception by Study Chair to continue on treatment until another scan time point (approximately 8 more weeks) if scans within first 6 months demonstrate radiographic progression to account for possible delayed responses on immunotherapy,⁴⁶ provided the patient is clinically stable or clinically improved (see Section 8.3.1).

Note: A subject with progression occurring between approximately 6-12 months (Cycles 8-16) on protocol therapy may be eligible for re-induction with GM-CSF if progression occurs after a documented response to prior induction (see Section 7.1.5.1).

- Unacceptable adverse experiences as described in Section 5.2.1.2.
- Intercurrent illness that prevents further administration of treatment.
- Investigator's decision to withdraw the subject.
- The subject has a confirmed positive serum pregnancy test.
- Noncompliance with trial treatment or procedure requirements.
- The subject is lost to follow-up.
- Completed 24 months of uninterrupted treatment with pembrolizumab or 35 administrations of study medication, whichever is later.

Note: 24 months of study medication is calculated from the date of first dose. Subjects who stop pembrolizumab at 24 months may be eligible for up to one year of additional study treatment as Second Course treatment if they progress within 6 months after stopping study treatment provided they meet the requirements detailed in Section 7.1.5.2.

- Administrative reasons

The End of Treatment and Follow-Up Phase procedures are listed in Section 6 (Protocol Flow Chart) and Section 7.1.5 (Visit Requirements). After the end of treatment, each subject will be

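### Whether a radiographic progression counts as a %PFS6 event depends on a discretionary, open-label decision to continue treatment, and the rule can only raise %PFS6 against its 20% null

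*Combined protocol and SAP*

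**What the plan says.** Three places bear on when a patient has progressed for %PFS6.

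- Section 4.3.6.2, under %PFS6: "Locally-assessed RECIST 1.1¹ will be used to determine progression". No confirmation requirement is mentioned there.
- Section 8.3.2(3), general definition: PFS runs from first dose "to date of first documented radiographic and/or clinical disease progression or death from any cause".
- Section 8.3.2(3), next paragraph, for patients who stay on treatment despite radiographic progression: "PFS will be calculated at time of first documented progression after subsequent imaging confirms progression". It continues: "If subsequent imaging does not demonstrate progression, then a PFS event will not have occurred".

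Section 5.8 says who can enter that last group: "A subject may be granted an exception by Study Chair to continue on treatment until another scan time point". This applies to scans in the first 6 months, in a patient who is clinically stable or better. Section 5.8 refers the reader to Section 8.3.1, but 8.3.1 defines ORR and has no rule on progression.

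Section 8.3.2(3) also says how censoring feeds the proportion: "Censored patients without progression will be treated as non-progression statistically and counted in denominator toward %PFS6".

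The duration-of-response definition in 8.3.2(4) ends at the first sign of progression and has no such exception. Sections 8.4.1 and 8.6.2.3 set %PFS6 against H0 20% and H1 40% with 40 evaluable patients.

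**The concern.** The general definition and the exception give different answers for the same scan. Take two patients with the same radiographic progression at week 8 and no progression on their next scan. If one was granted the exception and the other was not, the first has no event and the second is a %PFS6 failure. The deciding factor is a judgement made with full knowledge of treatment and clinical course, in the 6-month window that determines the endpoint.

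The effect has one direction. The exception can cancel an event but cannot create one, so %PFS6 under it is never below %PFS6 by first progression. The 20% comparator comes from retrospective chemotherapy series (Sections 4.1 and 4.3.6.2), and nothing in the documents says that progressions were removed there when a later scan did not show them. If some are removed here, part of any excess over 20% may come from the counting rule and not the treatment.

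There is also a gap. The exception is worded around what a later scan shows. It does not say what happens to a patient continued past progression who never has that scan.

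**Working it through.** **Inputs.** n=40 evaluable, H0 20%, H1 40%, stated power 78% (two-sided 5%) and 87% (one-sided 5%), from Sections 8.4.1 and 8.6.2.3. The documents do not give the number of patients whose progression is removed, nor a cut-off in patients. The cut-offs are derived below and the counts are assumptions.

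**Step 1: reproduce the plan's power.** Let X be the number progression-free at 6 months, X ~ Bin(40, p). Take the smallest cut-off whose upper tail at p=0.20 is within the allowed error.

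- One-sided 5%: P(X≥12 | 0.20)=0.0875 and P(X≥13 | 0.20)=0.0432, so the cut-off is 13. Power is P(X≥13 | 0.40)=0.871, against 87% stated.
- Two-sided 5%, 2.5% in the upper tail: P(X≥14 | 0.20)=0.0194, so the cut-off is 14. Power is P(X≥14 | 0.40)=0.789, against 78% stated.

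Both stated figures reproduce to within about one point with an exact one-sample binomial test.

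**Step 2: effect of converted patients.** Let X count patients progression-free by first progression, with true rate 20%. Suppose k patients who failed by first progression are counted as successes under the exception. The reported count is X+k, so the test succeeds when X ≥ c−k, with probability P(Bin(40, 0.20) ≥ c−k).

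| k (assumed) | c = 13 | c = 14 |
|---|---|---|
| 0 | 0.043 | 0.019 |
| 1 | 0.088 | 0.043 |
| 2 | 0.161 | 0.088 |
| 3 | 0.268 | 0.161 |

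Each converted patient adds 1/40 = 2.5 points to the observed %PFS6.

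**Step 3: a second model.** Treat the conversions as a shift in the underlying rate, from 20% to 22.5%, 25% or 27.5% (1, 2 or 3 expected patients in 40). The upper-tail error becomes 0.096, 0.179 or 0.291 at 13, and 0.049, 0.103 or 0.186 at 14. The conclusion is the same: about one converted patient in 40 roughly doubles the error.

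**Step 4: what k must mean.** k counts patients whose %PFS6 status actually changes. A patient counts only if the next scan does not show progression and there is then no later radiographic progression, clinical progression or death before 6 months. k is therefore no larger than the number of exceptions granted, and may be zero.

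**The case against.** The strongest reply is that this is a written, prespecified allowance for pseudo-progression under immunotherapy. Section 4.3.6.2 is a rationale section that names the measuring tool, while 8.3.2(3) is the operative definition, and a specific exception to a general rule is not a contradiction. That largely stands as a description of intent. It does not remove the dependence of event status on who was granted the exception, and it does not settle which version should face the 20%.

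Several stronger readings are tempting, and the documents do not support them.

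- *The null is a conventional-RECIST figure.* The progression criterion behind the 20% is not given, and one of the cited sources reports time on treatment (median 2.2 months, Section 4.1). What can be said is that no confirmation rule is stated for those series.
- *Progressions are simply erased.* The patient stays on scheduled imaging, and a later event before 6 months still makes a failure. A confirmed progression counts, and the natural reading of the dating sentence is that it counts from its first date, although the wording could be clearer.
- *A patient with no later scan is counted as a success.* The censoring text concerns patients without progression, and cancelling an event requires a later scan. This is an ambiguity, not a stated rule.
- *Stage 1 continued because of the exception.* Four of 9 were progression-free and 3 were needed, so two reclassified patients would have mattered. The documents do not say that any of the four relied on it.

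It is also fair that %PFS6 is now secondary and that Section 8.6.2 plans descriptive statistics for secondary endpoints. Even so, 8.4.1 and 8.6.2.3 call it a key secondary endpoint and give H0, H1 and power. Finally, changing the event definition after Stage 1 %PFS6 results are known needs to be declared.

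**Conclusion.** The point holds in limited form. For patients continued past radiographic progression, %PFS6 event status turns on an open-label, case-by-case decision. The rule departs from the RECIST 1.1 criterion stated in 4.3.6.2 and from the general definition in 8.3.2(3), and its effect on %PFS6 can only be upward or nil.

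The size is unknown because the documents give no rate of reclassification. The error rates above are illustrations, not estimates. They rest on 40 evaluable patients, a true first-progression %PFS6 of exactly 20%, the derived cut-offs of 13 and 14, and 1 to 3 patients whose 6-month status is truly changed. They show that very few such patients are enough to matter. They do not show that %PFS6 has been inflated. The primary ORR comparison is not touched. The point should be resolved before %PFS6 is compared with 20%.

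**What to change.** - In 8.3.2(3), for the comparison of %PFS6 with 20%, use first RECIST 1.1 or clinical progression, or death, as the event in every patient, whether or not treatment continued.
- Report the confirmation-based %PFS6 beside it as a sensitivity analysis, with the number of patients reclassified.
- State that a progression with no later scan stands as an event at its first date.
- Align 4.3.6.2 with 8.3.2(3), and correct the reference in 5.8, which now leads to the ORR definition.

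The cost is wording and one extra analysis on data already collected. The lead %PFS6 may be slightly lower. The amendment should note that the definition was settled after Stage 1 %PFS6 data were known; as the change can only lower the figure facing the null, it does not favour the treatment. Decisions about continuing treatment are unaffected.
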